This clinical trial will test the methodology and trial retention of one version of a combined therapy (along with comparison control groups). The combination of meditation and exercise will be done sequentially. This methodology is termed (1) Meditation first & then Exercise (Med&Exer). All participants in this exploratory trial will receive the therapeutic intervention, or one of three control options (negative control, meditation only, exercise only) (**Table 1**). We describe below the details of the interventions.

Table 1 – Experimental Conditions	
Experimental Condition	Description
Negative control	In clinic or at home, listen to an audiobook for ~15 minutes followed by 30 minutes of rest (including survey assessments)
Meditation only control	In clinic or at home, 15 minutes of meditation and listen to an audiobook for ~30 minutes (including survey assessments)
Exercise only control	In clinic or at home, listen to an audiobook for ~15 minutes (including survey assessments) then exercise (treadmill) for ~30 minutes
Meditation & then exercise (Med&Exer)	In clinic or at home, 15 min of meditation followed by 30 min of exercise (treadmill) plus survey assessments

Exercise in this exploratory study will consist of 30 minutes of moderate-intensity treadmill walking (starting at 3.5 mph and adjusted up or down to reflect moderate intensity for each individual participant) in the Rangos Human Testing Facility (Fisher Hall) on a treadmill with auto-shut off and integrated heart rate monitor (Polar H1 Heart Rate Sensor) on day 2 (first day of intervention), day 9, day 16, and day 23. During the other intervention days (day 3-6, 10-13, 23-27) participants will have the option of completing trials at Duquesne or “at home.” At home is defined as a participant using a personal treadmill or going to a community fitness center (e.g. YMCA). This “at home” component is designed to reduce the extra burden for patients who would otherwise have to travel to Duquesne for 22 total sessions (20 days of intervention plus intake and outtake sessions). Exercise will

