Title Page:

Statistical Analysis Plan

Combined exercise and meditation as a treatment for patients with chronic back pain

NCT number not available

12/21/17

Statistical Analysis Plan
Combined exercise and meditation as a treatment for patients with chronic back pain

This is a single-blind, single center randomized clinical trial comparing a treatment group (MedExT) versus a control group. The current analysis plan is specific to this study for reporting and publication purposes but is part of a larger study. The primary outcome of this study is to compare the post Roland-Morris Disability Questionnaire scores between the two independent groups. This will be achieved by comparing the mean post disability score for the MedExT group to the mean post disability score for the control group using a two-sample t-test (or the Mann-Whitney-Wilcoxon rank sum test if normality does not hold) in which a one-sided p-value < 0.05 will be considered a significant improvement in the MedExT group.

Three secondary treatment responses will be studied. The first will test whether the MedExT group will significantly increase mean scores on the Freiburg Mindfulness Inventory as determined by a two-sample t-test or the Rank Sum test given distributional properties of the data ($P < 0.05$). The second will explore whether the MedExT treatment will significantly influence a mean change in responses on the three psychological inventories administered; the Fear Avoidance Beliefs Questionnaire, the STAI state anxiety inventory and the STAI state trait inventory, $p < 0.02$. The third outcome measured will study mean response changes in the series of 14 Quantitative Sensory Tests measured at baseline and at the completion of the 4-week intervention period. Significant mean pre/post differences between groups will be identified using the two-sample t-test or the Rank Sum test where appropriate adjusting the significance level to 0.005. Additionally two pain outcome measures will be repeatedly observed throughout the study taken at baseline and on each intervention day. These measures are the VAS pain intensity score and the VAS pain unpleasantness. A repeated measures multivariate analysis of variance (MANOVA) procedure will be used to determine if the vector of timed responses is significantly different between the two study groups.

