The following demographic variables will be collected and compared between groups to further check against potential bias; age, sex, handedness, body mass index (BMI), baseline heart rate (HR), baseline blood pressure (BP), baseline IPAQ-short and mean number of steps taken per day over the 4-week intervention period. Difference in the proportion of sex/handedness will be tested using the Fisher's Exact test where a p-value less than 0.05 will be considered significant. All other continuous variables will be tested using the two-sample t-test to test for significance differences between the two study groups ($p < 0.05$).

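### Steps per day during treatment are tested as a baseline bias check, although they are measured after randomisation and may reflect the assigned walking

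*SAP*

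**What the plan says.** The last paragraph of the SAP opens: "The following demographic variables will be collected and compared between groups to further check against potential bias". Eight items follow: age, sex, handedness, BMI, heart rate, blood pressure, IPAQ-short and the "mean number of steps taken per day over the 4-week intervention period". Heart rate, blood pressure and IPAQ-short are each marked as baseline. Steps are not, and their window is the treatment period. Sex and handedness go to Fisher's exact test. For the rest: "All other continuous variables will be tested using the two-sample t-test to test for significance differences between the two study groups", at p < 0.05. The SAP does not say what follows from a significant result.

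The SAP describes the trial as "comparing a treatment group (MedExT) versus a control group" without saying which of the protocol's three controls is meant. In the protocol (section 3, Intervention Sessions and Table 1) the combined arm has "30 minutes of moderate-intensity treadmill walking" per session, "starting at 3.5 mph and adjusted up or down to reflect moderate intensity for each individual participant", five times a week for four weeks. The exercise-only control has the same walking. The negative and meditation-only controls have none. Wrist activity monitors are worn throughout the four weeks (protocol section 4, Assessment - Exercise).

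Baseline RMDQ is not in the list, although the primary analysis compares post-treatment RMDQ means without adjustment.

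**The concern.** A balance check asks whether the groups were alike before treatment could act. Only variables fixed before randomisation can answer that. Steps counted during the intervention are affected by the assignment itself wherever one arm is told to walk and the other is not.

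The check can therefore mislead in both directions. A significant difference may show only that the walking was done, yet under the SAP's wording it would count as evidence of possible bias. A null result would look reassuring, yet it could mean poor adherence or less walking at other times of day. At stake is what the trial report says about comparability of the arms, and whether someone later feels obliged to adjust for a consequence of treatment.

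The other tests in the paragraph have a smaller fault. In a properly randomised trial, a p-value on a true baseline variable can flag only chance. Meanwhile the baseline variable most relevant to the primary outcome is absent from the list.

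**Working it through.** The documents give no sample size, expected step count or SD, so there is no planned figure to reproduce. The timing point follows from the text alone. The arithmetic shows only how often the check could misfire.

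**Inputs from the documents**
- Session: 30 minutes, starting at 3.5 mph (protocol section 3).
- Sessions: 20 over four weeks, taken as 28 days.
- Adherence needed for the exit session: at least 80% (protocol section 6). 0.80 × 20 = 16; the protocol's own gloss says more than 16, so 16 is a slightly low lower end.
- Test: two-sample t-test at 0.05, taken as two-sided because no side is stated.

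**Assumptions**
- 2,000 to 2,250 steps per mile.
- 3.5 mph throughout, although the protocol lets speed vary by participant.
- Full capture by the monitor and no offsetting fall in other walking.
- Between-person SD of 2,500 to 4,500 steps per day.
- 20 participants per arm.
- A control arm without walking.

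**Added steps per day**
- Distance per session: 3.5 × 0.5 = 1.75 miles.
- Steps per session: 1.75 × 2,000 = 3,500, to 1.75 × 2,250 = 3,938.
- All 20 sessions: 3,500 × 20/28 = 2,500, to 3,938 × 20/28 = 2,813.
- 16 sessions: 3,500 × 16/28 = 2,000, to 3,938 × 16/28 = 2,250.
- Overall, about 2,000 to 2,800 per day.

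**Chance that the test flags this difference in a fair trial**

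The t statistic has noncentrality (difference / SD) × √(n/2), with 38 degrees of freedom and critical value 2.024. For n = 20, √(n/2) = 3.162. For example, (2,500/2,500) × 3.162 = 3.162 gives 87%, and (2,000/4,500) × 3.162 = 1.405 gives 28%.

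| Difference (steps/day) | SD 2,500 | SD 3,500 | SD 4,500 |
|---|---|---|---|
| 2,000 | 69% | 42% | 28% |
| 2,500 | 87% | 60% | 40% |

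Over the same differences and SDs the range is about 16% to 56% at 10 per arm and 50% to 99% at 40 per arm. A valid balance test would flag 5%.

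**False alarms among the seven true baseline variables**
- Five are continuous, counting blood pressure once: 1 − 0.95^5 = 23%.
- Fisher's exact test is conservative. At 20 per arm its true size is about 2% for a 50% proportion (assumed for sex) and about 1% for a 90% proportion (assumed for handedness).
- Together, if independent: 1 − 0.95^5 × 0.98 × 0.99 = 1 − 0.7738 × 0.9702 = 25%.

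**Baseline RMDQ**

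Protocol section 4 defines the primary outcome as a fall in RMDQ disability, which needs a pre-treatment value. It does not state when the RMDQ is given. The SAP does say that the VAS pain scores are taken at baseline.

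**The case against.** **No analysis depends on the step comparison.** A reader might infer that the SAP will adjust for steps and so remove part of the treatment effect, or that the primary result is compromised. The documents do not support that. The SAP lists a comparison, with no covariate, exclusion or decision rule attached, and the primary t-test (or rank sum test) is unaffected. This stands, and it limits the harm to interpretation and reporting.

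**The comparator is not named.** A reader might also infer that a large difference in steps is bound to appear. If the control is exercise-only, both arms have the same prescribed walking and the expected difference largely disappears. This stands too. It removes the size of the problem in that case, but not the fault in timing.

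**Activity during treatment can bear on bias.** Controls who take up walking by themselves would be a form of contamination, and monitors worn for four weeks could reveal it. That is a sensible use of the data. But the SAP places the variable among demographics and does not separate prescribed sessions from other activity, so a raw difference in total steps cannot isolate contamination.

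**The size rests on assumptions.** SD, sample size, steps per mile and the absence of compensation all come from outside the documents, so no single percentage should be quoted. Nor should the false-alarm rate be put at 1 − 0.95^7 = 30%, which gives the two Fisher tests a full 5% size. Correlation among the baseline variables would also change the 25%.

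**Baseline tests do no harm if nothing is conditioned on them.** This is largely true; the case for dropping them is that they tell the reader nothing useful.

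**Conclusion.** The point holds as a fault of classification and interpretation. Intervention-period steps are a post-randomisation variable and cannot serve as a baseline bias check, whichever control is used. That conclusion needs no assumption.

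The likely size depends on the comparator. Against the negative or meditation-only arm, the assigned walking would be expected to add roughly 2,000 to 2,800 steps per day. At an assumed 20 per arm, the check would then signal bias in about 28% to 87% of fair trials for differences of 2,000 to 2,500 and SDs of 2,500 to 4,500. That walking sessions raise total daily steps is inferred from the design; the documents do not state it. Against exercise-only, little treatment-driven difference is expected.

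Testing the seven true baseline variables adds about a 25% chance of at least one false alarm under independence, while an imbalance in baseline RMDQ would be neither shown nor corrected. The change is worth making because it costs little, but the planned primary test is not invalid for this reason.

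**What to change.** 1. Remove intervention-period steps from the list of variables "compared between groups to further check against potential bias". Report them by arm, with mean and SD, as an adherence or process measure. If the monitor data allow, separate prescribed sessions from other activity, which would also serve as a contamination check. State that steps will not be a covariate in any treatment comparison.
2. Name the control arm, so that the step data can be interpreted.
3. Present the true baseline variables descriptively, without p-values, and add baseline RMDQ and baseline pain VAS to the table.
4. Confirm that the RMDQ is collected at intake. If so, pre-specify that the post-treatment comparison is adjusted for baseline RMDQ (for example, a linear model with arm and baseline score), whatever any balance comparison shows.

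Items 1 to 3 are changes of SAP wording and use data already planned. Item 4 changes the primary method and so belongs in a SAP amendment made before outcomes are examined by arm. It needs no new data if the intake RMDQ exists.
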